10.4 DESCRIPTION OF STATISTICAL METHODS

10.4.1 GENERAL APPROACH

The design of this study is a three-period crossover design, where each of three study periods is a perimenstrual frame of the menstrual cycle (days +7 to +22 following ovulation where positive ovulation test day=0). Each participant will complete all three conditions in a randomized order.

Primary hypothesis tests will be evaluated using a alpha level of .05, with a two-tailed test.

All outcomes will be checked for normality; given the low likelihood that suicidality will follow a normal distribution even in this clinical sample, we expect that we will need to utilize nonparametric procedures.

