10.3 ANALYSIS DATASETS

An intent-to-treat dataset will be utilized. The study statistician will use a carry-forward approach to evaluate the within-person condition effect using this intent-to-treat sample.

CLEAR 2 Study Protocol: Hormones and Suicide Risk, Version 9, 07-02-2020, Page 42 of 64

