10.4.2 ANALYSIS OF THE PRIMARY EFFICACY ENDPOINT(S)

Primary and secondary endpoints are operationalized above (i.e., mean within-person differences between conditions) for the daily SITB suicidal ideation and planning subscales (primary endpoints) as well as the daily UPPS-P impulsivity, PROMIS anxiety, CESD depression, BHI hopelessness, and SSES rejection sensitivity subscales (secondary endpoints).

Analyses will proceed identically for all outcomes listed above. First, we will calculate each subject's mean daily rating (via phone) on the outcome measure *during* each condition.

Second, we will utilize repeated measures ANCOVA to examine the within-person condition effects. Covariates (medicines, BMI, age) will be examined and included. These analyses will be conducted on the intent-to-treat dataset.

If necessary due to violations of model assumptions, we will utilize similar nonparametric tests.

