10.5 SAMPLE SIZE

An unlimited number of potential participants will be screened. 60 females will be enrolled in the study, with the goal of 40 participants completing the study.

Power analyses are described below; alpha is set at .05, power at 80%. The null hypothesis is no link between the study experimental condition and risk for suicidal ideation, intent, and planning; the alternate hypothesis is that hormone stabilization in the experimental condition will prevent flux in these suicide-related outcomes. Because no previous studies have examined the impact of experimental hormones on suicidality, we have conducted power analyses using existing effect sizes on related constructs (e.g., BPD features).

Power Analysis. For primary hypothesis tests, 80% power to detect a conventionally mediumsized effect of condition (f = .25) is achieved with 24 participants¹¹⁷. To allow for attrition and improve generalizability and power, we propose to include 40 participants in the final sample.

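### The choice of primary test hangs on a normality check of the outcomes themselves, which is the wrong diagnostic for a within-person contrast and leaves the primary test unfixed

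*Combined protocol and SAP*

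**What the plan says.** Section 10.4.1 states: "All outcomes will be checked for normality". It considers a normal distribution of suicidality unlikely even in this sample, and continues: "we expect that we will need to utilize nonparametric procedures".

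Section 10.4.2 averages each woman's daily ratings within each condition and then says "we will utilize repeated measures ANCOVA to examine the within-person condition effects". On covariates: "Covariates (medicines, BMI, age) will be examined and included". The analysis is placed on the intent-to-treat dataset. A second trigger follows: "If necessary due to violations of model assumptions, we will utilize similar nonparametric tests".

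No normality test, threshold, decision rule or replacement test is named in either section, and Section 10.1 rules out a formal SAP.

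Three other places bear on the point:

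- Section 10.3, on incomplete data: "The study statistician will use a carry-forward approach to evaluate the within-person condition effect using this intent-to-treat sample".
- Sections 4.1 and 6.1.9 describe multilevel models instead, the latter because they tolerate missing data.
- Section 10.5, on sample size: "80% power to detect a conventionally mediumsized effect of condition (f = .25) is achieved with 24 participants". It aims for 40 completers out of 60 enrolled.

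**The concern.** The primary endpoints in Section 4.2.1 are within-person differences between conditions. A woman's stable level of suicidality enters all three of her condition means and drops out of every difference. Whether the F test is trustworthy therefore depends on the within-person residuals, not on how the scores are distributed across women. A sample with a few severely ill women and many mildly ill ones will look skewed even when the within-person differences are well behaved.

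Two things are at stake. First, the primary test is not fixed in advance: an undefined check on the trial's own data selects between a named analysis and an unnamed one. Second, the check can fire when nothing is wrong with the planned analysis. The cost then depends on what replaces it, which the reader cannot know.

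**Working it through.** **Inputs from the documents.** k = 3 conditions; f = .25; two-sided alpha .05; 24 participants for 80% power; 40 completers (10.4.1, 10.5).

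**Assumptions.** The within-person correlation rho is not stated; .5 is used, with the range shown in step 1. The fallback is not named; Friedman's test is used as the usual rank test for three conditions. The effect pattern is A = B > C, as hypothesised in 10.2.

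**1. The plan's own figure.** For a within-subject factor, lambda = f² × n × k / (1 − rho), with df = k − 1 and (n − 1)(k − 1).

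- n = 24: lambda = .0625 × 24 × 3 / .5 = 9.0; df 2, 46; power 74.1%.
- n = 28: lambda = 10.5; df 2, 54; power 81.2%.
- n = 40: lambda = 15.0; df 2, 78; power 93.5%.

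At rho = .5 the number needed is 28, not 24. It is 38 at rho = .3, 25 at .55, 23 at .6 and 17 at .7. The stated 24 is reproduced with three conditions if rho is about .56. Either way, the figure belongs to a parametric F test.

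**2. Does the check look at the right quantity?** Simulation with exponential woman levels, normal within-person errors and rho = .5.

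| Quantity, n = 40 | Result |
|---|---|
| Shapiro test rejects at least one condition's scores | about 53% of trials |
| Shapiro test rejects a within-person difference | about 5% |
| Type I error of the F test | about 5% |

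A separate run set up independently gave 46% on the scores and 4% on the residuals, with an F-test size of 4.9%. In both runs the check on scores fires in about half of trials in which the F test is sound.

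**3. Cost of a needless switch.** Under normality, the asymptotic efficiency of Friedman relative to F is (3/π) × k/(k + 1) = 9/(4π) = .716. So 40 women act like 40 × .716 = 28.6, and 24 would have to become 24 / .716 = 33.5, that is 34. Simulated power with normal errors:

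| n | F | Friedman |
|---|---|---|
| 24 | about 74% | about 60% |
| 40 | about 93% | 82–83% |

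If rho is raised to .573, so that F has 81% at 24, Friedman has 68% there and 89% at 40.

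**4. When within-person errors are not normal (n = 40).**

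| Within-person errors or score | F | Friedman |
|---|---|---|
| Laplace | 94% | 93% |
| t with 3 df | 94% | 98% |
| Floored count score, about 18% zeros (assumed) | 80.3% | 78.1% |

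The floored row uses an effect chosen to give F about 80%. The advantage of F disappears or reverses once the errors themselves are heavy-tailed, and is about two points with flooring.

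**The case against.** The strongest reply has four parts.

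- **The check may be aimed correctly.** The endpoints are defined as within-person differences, so a check of all outcomes could mean those differences, and 10.4.2 ties its fallback to model assumptions. The wording does leave this open. But the reason given in 10.4.1 is that suicidality itself is unlikely to be normal, which points to the scores. The second trigger does not withdraw the first, and neither comes with a rule.
- **Friedman is not in the plan.** Correct. Permutation or rank-based covariance methods also fit the wording, so the power figures are conditional on that choice. That the primary test has to be guessed is itself the defect.
- **Rank tests may suit these data.** This stands. The plan anticipates non-normal scores, and step 4 shows no general loss.
- **The planned size absorbs the loss.** This stands too: 40 completers keep 82–89% under Friedman.

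A reader might also infer that the fallback discards women with a missing condition and so becomes a complete-case analysis. The documents do not support that. Section 10.3 carries values forward, so those women are imputed, and classical repeated measures ANCOVA needs complete rows as well. Nor is the loss of covariates a serious harm. A standard Friedman test cannot carry them, but age and BMI are nearly constant within a woman and barely affect a within-person contrast; medication matters only if it changes during the study.

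**Conclusion.** The concern holds in a limited form. Section 10.4.1 directs its check at the outcomes and expects to leave the named analysis on the strength of it. For a within-person contrast that is the wrong diagnostic; it makes the primary test data-dependent and can trigger an unnecessary switch. If the fallback is Friedman's test and within-person errors are normal (f = .25, rho = .5), the price is about 11 points of power at 40 completers (93% to 82%) and about 14 at 24 (74% to 60%).

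It would go too far to say that power falls below target at the planned size, or that the rank test is generally inferior. With 40 completers the 80% target is still met, and with heavy-tailed or floored scores the two tests are about equal or the rank test is better. The trigger rate of roughly one half also rests on the assumed skew between women. What does not rest on the simulation is that no test, threshold or rule is specified.

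**What to change.** In 10.4.1 and 10.4.2:

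- Delete the normality-of-outcomes trigger and the open-ended fallback.
- Prespecify one primary model on the condition means, with condition and period effects, fitted to the observed data. This agrees with the multilevel models in 4.1 and 6.1.9.
- Reconcile that model with the ANCOVA in 10.4.2 and the carry-forward in 10.3. Carrying forward in a crossover copies one condition's value into another. In an illustration with 60 women, 10 missing one period and 10 missing two, it shrank the A/B minus C contrast from 0.53 to 0.40.
- Report the mean difference that defines the endpoint, with a p-value from re-randomisation over the six condition orders (following the allocation scheme actually used) and a participant-level bootstrap confidence interval. Neither relies on normality.
- Inspect within-person residuals as a diagnostic only, and keep a rank test such as Friedman's as a sensitivity analysis.
- In 10.5, state the correlation behind the 24.

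Cost: a paragraph or two of text and a short script; no new data. The downside is possibly slightly less power than a rank test if within-person errors are heavy-tailed.

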10.4.2 ANALYSIS OF THE PRIMARY EFFICACY ENDPOINT(S)

Primary and secondary endpoints are operationalized above (i.e., mean within-person differences between conditions) for the daily SITB suicidal ideation and planning subscales (primary endpoints) as well as the daily UPPS-P impulsivity, PROMIS anxiety, CESD depression, BHI hopelessness, and SSES rejection sensitivity subscales (secondary endpoints).

Analyses will proceed identically for all outcomes listed above. First, we will calculate each subject's mean daily rating (via phone) on the outcome measure *during* each condition.

Second, we will utilize repeated measures ANCOVA to examine the within-person condition effects. Covariates (medicines, BMI, age) will be examined and included. These analyses will be conducted on the intent-to-treat dataset.

If necessary due to violations of model assumptions, we will utilize similar nonparametric tests.

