 - **Justification**: These factors are known sources of variability in suicidality and would therefore introduce error into our models as well as increasing the risk that a participant would experience

CLEAR 2 Study Protocol: Hormones and Suicide Risk, Version 9, 07-02-2020, Page 16 of 64

a suicidal crisis during the study^{17,100}. Use of opioids, methamphetamine, and cocaine will be screened at the enrollment visit to validate self-report measures of substance use.

13. Must report at least some recent suicidal ideation (in the past month) at enrollment.

- Justification: As reviewed in the research strategy, the purpose of the study is to examine the impact of natural perimenstrual hormone withdrawal (vs. prevention of either E2 or P4 withdrawal) on within-person changes in suicide risk. The present sampling strategy **ensures** generalizability²⁴ of our findings to clinical populations of interest and will also prevent a floor effect (i.e., zero-inflation of daily outcome measures and associated limitations in power to detect effects) on primary daily outcome measures (e.g., mediating behavioral constructs, suicidality).

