10.4.6 BASELINE DESCRIPTIVE STATISTICS

Groups (counterbalanced orders) will be compared on demographic factors such as age, severity of perimenstrual mood change in the placebo condition, and general suicidality. However, inferential statistics are not necessary as our primary outcome modeling procedures will control for any baseline differences that exist.

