10.6 MEASURES TO MINIMIZE BIAS

10.6.1 ENROLLMENT/ RANDOMIZATION/ MASKING PROCEDURES

Individuals will be enrolled following phone screen and an enrollment visit as described above. Individuals will be randomized by IDS to one of six condition orders (permutations of A-B-C) following enrollment visit if they meet study criteria and give informed consent. Masking and blinding will be handled by IDS according to standard procedures for double blinding, and will be

CLEAR 2 Study Protocol: Hormones and Suicide Risk, Version 9, 07-02-2020, Page 46 of 64

fully double-blind. Randomization codes will be kept by IDS until the completion of the study, and will be shared only as needed for unblinding as needed for safety monitoring (described above).

Blinding and Compliance: Pills are dispensed in a double-blind manner. Patches will be placed by CTSA staff at UIC. All study staff will remain blinded. Preliminary analyses from the preceding similar experiment revealed that the blinding was successful; participants were not more likely to report believing they were on active treatment in the active condition relative to the placebo condition (p = .58). Participants will: **1**) be educated on the importance of compliance; **2**) be asked about compliance on each daily call; and **3**) have steroid levels measured to confirm compliance.

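### The primary analysis of a three-period crossover names no period term, so any drift over the 6-7 months goes into the within-person error and costs power

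*Combined protocol and SAP*

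**What the plan says.** Section 10.4.1 states: "The design of this study is a three-period crossover design". Section 10.6.1 has participants "randomized by IDS to one of six condition orders", the permutations of A, B and C. No blocking or equal-allocation rule is stated.

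Section 10.4.2 first averages each participant's daily telephone ratings within each condition. It then continues: "Second, we will utilize repeated measures ANCOVA to examine the within-person condition effects. Covariates (medicines, BMI, age) will be examined and included". Similar nonparametric tests are the fallback, and section 10.4.1 expects to need them, but none is named.

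Section 4.1 describes a multilevel model instead, with condition and possibly condition by day; it has no period term either. Section 10.4.6 says the order groups will be compared descriptively because "our primary outcome modeling procedures will control for any baseline differences that exist", without naming the term that would do this. Section 10.1 says there will be no formal SAP.

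**The concern.** A crossover separates the condition effect from the effect of time by giving each condition in each period. The analysis gets the full benefit only if period is in the model. Here three facts make a time trend plausible: participants are selected because they "Must report at least some recent suicidal ideation (in the past month) at enrollment", they stay under outpatient care, and they are rated repeatedly over roughly 6-7 months. The washout cycle between conditions deals with carryover, not with a trend over the study.

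Without a period term, any trend common to all participants is counted as unexplained within-person variation. The named covariates do not help. Age, BMI and medication at enrolment are fixed within a person and cancel from a within-person comparison. The assurance in section 10.4.6 does not help either, since drift across periods is not a baseline difference between order groups. At stake is precision for the primary condition contrasts.

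**Working it through.** **Inputs from the documents.** "Primary hypothesis tests will be evaluated using a alpha level of .05, with a two-tailed test" (section 10.4.1); "alpha is set at .05, power at 80"% and "effect of condition (f = .25) is achieved with 24 participants" (section 10.5); 60 enrolled and 40 completers (section 10.5); three conditions and six orders (sections 10.4.1 and 10.6.1).

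**Assumptions not in the documents.** Correlation between conditions rho = .5 (range .3 to .7); sphericity; normal errors; linear drift of d total SDs per period, with d = 0, .25 or .5 (2d over the study); loss unrelated to order or condition.

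**1. The plan's own figure.** For a within-person factor with m = 3 levels, the noncentrality is lambda = f² × N × m / (1 − rho), with m − 1 and (N − 1)(m − 1) degrees of freedom.
- N = 24, rho = .5: lambda = .0625 × 24 × 3 / .5 = 9 on 2 and 46 df. Power is 74%, and 80% needs N = 28.
- N = 24 is reproduced at rho = .58: lambda = 4.5 / .42 = 10.7, power 82%. The plan does not state its correlation.
- N = 40, rho = .5: lambda = .0625 × 40 × 3 / .5 = 15 on 2 and 78 df. Power is 93.5%.

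**2. How drift enters the error.** With balanced orders, period effects −d, 0, +d add N × 2d² to the residual sum of squares on 2(N − 1) df. Relative to the within-person variance 1 − rho, the inflation is N × d² / [(N − 1)(1 − rho)].
- d = 0: none.
- d = .25: 40 × .0625 / (39 × .5) = 2.5 / 19.5 = 13% (9% at rho = .3, 21% at rho = .7).
- d = .5: 40 × .25 / (39 × .5) = 10 / 19.5 = 51% (37% to 86%).

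**3. Effect on the test.** Simulated trials with f = .25 (f = 0 for type I error), rho = .5, orders balanced at 60 and random loss to 40:

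| Drift per period | Power, no period term | Power, with period term | Type I error, no period term |
|---|---|---|---|
| 0 | 94% | 94% | about 5% |
| .25 SD | 91% | 93% | 3.4% |
| .5 SD | 81% | 93% | 1.8% |

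Type I error with period in the model stays at about 5%. The omitted-period test is conservative because near-balance largely keeps drift out of the condition estimates while the error estimate still absorbs it.

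**4. Unequal order counts.** With random loss from 60 to 40 at .5 SD per period, the mean error of the A minus C estimate under the null was 0.003 to 0.004 SD, in effect zero. The cost is noise. Under simple randomisation of 40, the SD of that estimate is 0.197 without period and 0.163 with it, power is 79% against 93%, and type I error without period stays near 5%.

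**5. Covariates.** A person-constant covariate can affect a within-person contrast only through its interaction with condition. If the software fits those interactions with uncentred values, the condition main effect is the effect at age 0 and BMI 0. Assuming age 30 (SD 7), BMI 24 (SD 3), half medicated and N = 40, power is 93.7% with no covariates, 93.6% centred and 5.9% uncentred. Section 10.4.2 does not say which form will be used.

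**The case against.** The best defence is that the design already does most of the work. All six orders are used, washout cycles separate the conditions, and the documents give no estimate of drift. With 40 completers, power stays near or above the 80% target even at 1 SD of drift over the study (79% to 81%, depending on how orders are allocated), and with balanced orders the error is towards caution, not false positives. All of this stands and limits the size of the point. Section 4.1 still mentions 30 participants, where the loss would be larger (about 67% against 84% at .5 SD per period), but section 10.5 plans for 40.

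Several stronger readings are tempting, and the documents do not support them:
- *The error term is inflated as the plan stands.* It is inflated only if scores drift.
- *Loss from 60 to 40 turns drift into bias.* Bias would need loss related to order or condition, and nothing in the documents indicates that.
- *The missing order term inflates the error.* Order is a between-person factor and does not change within-person error.
- *The covariates ruin the condition test.* The 5.9% figure describes one uncentred coding with condition interactions. With covariate main effects only, centring would not matter.
- *The covariates should be dropped.* Section 4.1 gives a reason for covarying medication, and centring is enough.

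The normal-theory figures may also not describe a nonparametric fallback. That is fair, and is a reason to specify how the fallback handles period.

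**Conclusion.** The gap is real and modest. No section names a period term for a three-period crossover. The loss is nil without drift, about 2 percentage points of power at .25 SD per period and about 12 at .5 SD per period. These sizes rest on f = .25, correlation .5, sphericity, linear drift and random loss to 40 completers; a higher correlation makes the relative inflation of the error larger. The carry-forward of missing data in section 10.3 was not modelled. The absence of a centring rule is a separate ambiguity: it could matter greatly under one coding and not at all under another, and the plan does not say which applies.

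**What to change.** In section 10.4.2, replace the second step with a linear mixed model that has condition and period (1 to 3) as fixed effects and participant as a random effect. Keep the planned covariates, with age and BMI centred at their sample means and medication taken as recorded at enrolment. Section 7.5 records medication throughout, and a value recorded during treatment could itself be affected by condition. Randomised order may be added but is not needed for within-person precision.

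Name the nonparametric fallback in sections 10.4.1 and 10.4.2 and require it to account for period. An ordinary rank test for related samples would ignore period and could not take the covariates. Bring the multilevel model in section 4.1 into line.

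The cost is a change of wording before analysis and two degrees of freedom. With no drift, power at 40 completers is 93.5% with or without the period term.

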Design Overview: 40 female patients (up to 60 enrolled to allow for dropout) with recent suicidal ideation but minimal^{17,18} imminent risk for suicide attempt will complete behavioral tasks and clinical risk assessments in **three** conditions: **(A) perimenstrual E2/P4 withdrawal** (under placebo), **(B) perimenstrual P4 withdrawal** (during exogenous perimenstrual stabilization of E2 only) and **(C) perimenstrual E2 withdrawal** (during exogenous perimenstrual stabilization of P4 only). Mediation by degree of perimenstrual ALLO withdrawal will be explored for significant condition contrasts.

CENTRAL HYPOTHESIS: Test the hypothesis that key suicide risk pathways will be heightened during conditions involving P4 withdrawal (conditions A and B above) relative to the E2 withdrawal condition (condition C), and that this greater risk will be mediated by a steeper slope of withdrawal from ALLO during P4 withdrawal and natural (placebo) E2/P4 withdrawal conditions relative to E2 withdrawal condition (where P4 is stabilized).

JUSTIFICATION OF E2/P4 DOSING AND SCHEDULE

Chosen formulations are bioidentical to human E2 and P4 and were selected to mimic luteal phase concentrations or E2 and P4. Results from the PI's recently-completed similar experiment indicate that these doses were effective in stabilizing (rather than increasing) luteal phase levels.

Rationale for Route and Dose of E2 and P4. We will use Climara® 7 day transdermal E2 patches. Peak levels of E2 with Climara (~45 pg/mL), achieved within 24 hrs., correspond to luteal E2 levels¹⁰². No transdermal P4 is available. Although transdermal synthetic progestins are available, these molecules have a high affinity for androgen and mineralocorticoid receptors, limiting their usefulness for testing hypotheses. Thus, oral prometrium will be dosed b.i.d. to achieve luteal P4 levels (~13 ng/dL)¹⁰² to create **steady-state levels**.

Rationale for Duration of E2/P4. Administration for 14 days starting 7 days after ovulation will span the range of time in which natural perimenstrual withdrawal would occur and prevent natural withdrawal of *either E2 or P4*.

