3 OBJECTIVES AND PURPOSE

The purpose of this mechanistic study is to experimentally test a pathophysiologic mediational model in which late luteal (perimenstrual) ovarian steroid withdrawal increases suicidal desire (via increased hopelessness and negative social appraisals) and suicidal action capacity (via reduced inhibitory control and increased threat sensitivity). We predict that natural P4 withdrawal (compared to the two conditions in which P4 is stabilized) will increase reports of suicidal desire (partially mediated by task performance indicating increased hopelessness and negative social appraisals) and action capacity (partially mediated by task performance indicating increased hopelessness and negative social appraisals) and action capacity (partially mediated by task performance indicating decreased inhibitory control and increased threat sensitivity). Therefore, we predict that administration of P4 will reduce suicide risk by buffering the deleterious impact of perimenstrual withdrawal from P4. We predict that administration of E2 will have some mild protective effects, but not to the same extent as P4.

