Primary Windows of Comparison for Hypothesis Testing. To test whether prevention of P4 withdrawal (in Condition C) reduces the perimenstrual increase in suicide risk, **primary** hypothesis tests will compare degree of suicide risk (as measured with self-report, tasks, and interviews) during the perimenstrual weeks of each condition (days +7 to +22). **Secondary** analyses will examine Condition C, testing whether tapered withdrawal from exogenous P4 around days +16 to +22 causes "shifted"/"postponed" perimenstrual risk.

Hypotheses/Analytic Plan. It is hypothesized that Condition A (E2/P4 withdrawal under placebo) and Condition B (P4 withdrawal under E2 stabilization) will BOTH be associated with heightened perimenstrual suicidality, but that Condition C (E2 withdrawal under P4 stabilization) will significantly reduce perimenstrual increases in suicidality. We also hypothesize that a steeper slope of ALLO withdrawal, calculated across the lab ALLO measures in each condition, will mediate the more deleterious effects of P4 withdrawal conditions. Multilevel models will be used (repeated observations nested within individuals) to predict daily or weekly repeated suicidality and mediator outcomes from a within-person condition factor (and, if appropriate, the interaction of condition and day). Mediation by degree of ALLO withdrawal will be tested by estimating a 95% CI for the indirect effect of condition (focal predictor) on suicide risk outcomes (dependent variable) via the slope of ALLO change across the perimenstrual phase (mediator). **Power Analysis**. For primary hypothesis tests, 80% power to detect a conventionally medium-sized effect of condition (f = .25) is achieved with 24 participants¹¹⁷. To allow for attrition and improve generalizability and power, we propose to include 30 participants.

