4.2.1 PRIMARY ENDPOINT

The primary endpoints (described below) of this mechanistic study are suicidal ideation and planning score differences between placebo condition and stabilization conditions on the SITBI measure. These were chosen given their strong predictive validity in epidemiological studies.

(1) Mean Within-Person Condition Differences (7 final placebo days – 7 final stabilization days) of SITB Suicidal Ideation subscale score

CLEAR 2 Study Protocol: Hormones and Suicide Risk, Version 9, 07-02-2020, Page 14 of 64

(2) Mean Within-Person Condition Differences (7 final placebo days – 7 final stabilization days) of SITB Suicidal Planning subscale score

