10.2 STATISTICAL HYPOTHESES

Hypotheses. For suicidal desire and suicidal action capacity—our primary endpoints)—we predict that perimenstrual increases in suicidal desire and action capacity (Lab 2 – Lab 1 within each condition) will be larger in the placebo (natural E2 + P4 withdrawal) condition and experimental E2 stabilization (P4 withdrawal) condition than in the experimental P4 stabilization (E2 withdrawal) condition. The associated null hypothesis is that there will be no difference in the perimenstrual increase in suicidality across conditions. For our secondary endpoints, including hopelessness, negative social appraisals, reduced inhibitory control, and threat sensitivity, we predict the same pattern of results.

There are no "efficacy" endpoints in the present trial since it is mechanistic and not a treatment study.

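### The prediction is that suicidality is lower in C than in both A and B, but the null, primary ANCOVA and power are written for a general condition effect, and no primary contrast or decision rule is named

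*Combined protocol and SAP*

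**What the plan says.** Conditions: A is placebo (both hormones withdraw), B is E2 stabilization (P4 withdraws), C is P4 stabilization (E2 withdraws).

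**Prediction.** Section 4.1 says A and B "will BOTH be associated with heightened perimenstrual suicidality" while C reduces it. The central hypothesis in 2.2 and the hypotheses in 10.2 have the same shape. Section 3 adds: "We predict that administration of E2 will have some mild protective effects, but not to the same extent as P4".

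**Null, analysis and power.**
- 10.2: "The associated null hypothesis is that there will be no difference in the perimenstrual increase in suicidality across conditions". The null in 10.5 is likewise no link between condition and risk.
- 10.4.2: after averaging the daily ratings, "we will utilize repeated measures ANCOVA to examine the within-person condition effects".
- 10.4.1: "Primary hypothesis tests will be evaluated using a alpha level of .05, with a two-tailed test". It also expects nonparametric procedures to be needed.
- 10.5: 24 participants give 80% power for an effect of condition of f = .25; the target is 40 completers.
- 10.4.9 (multiplicity) is marked not applicable, and 10.1 states that no formal SAP will exist.

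**Contrasts.** Section 2.2 says that mediation "will be explored for significant condition contrasts", without listing them. The multilevel model in 4.1 predicts suicidality and "mediator outcomes from a within-person condition factor".

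**Primary endpoints.** Section 4.2.1 defines two, as "suicidal ideation and planning score differences between placebo condition and stabilization conditions", each calculated as placebo minus stabilization. The Protocol Summary uses the same formula but adds that it applies across all three conditions, and 10.4.2 restates it as differences between conditions.

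**The concern.** The scientific claim needs two specific comparisons. C against A asks whether preventing P4 withdrawal lowers risk relative to the natural cycle. C against B asks whether it does so more than preventing E2 withdrawal, which is the only comparison that tests the statement in section 3. A significant general condition effect establishes neither.

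Without a stated rule, a positive primary result could come from E2 alone, from both hormones equally, or from P4 alone. The choice of decisive contrast would then be open after unblinding. The placebo-minus-stabilization formula adds to the ambiguity because B and C are both stabilization conditions. With two primary endpoints, the plan also does not say whether one or both must succeed.

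**Working it through.** **Inputs.** From the documents: two-sided .05, f = .25, 24 participants for 80% power (10.4.1, 10.5), 40 completers (10.5), three conditions. Not given: the correlation rho between conditions, and the pattern of means. I assume rho = .5 and show .3 and .7. SD is set to 1, with equal correlations and normal data.

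**The plan's own figure.** For a one-group, three-condition F test, lambda = N x 3 x f^2 / (1 - rho), with 2 and 2(N - 1) degrees of freedom.
- N = 24, rho = .5: lambda = 24 x 3 x .0625 / .5 = 9.0; power 74%.
- N = 24, rho = .57: lambda = 4.5 / .43 = 10.5; power 81%.

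So 24 is reproduced as a three-condition test at rho of about .57. It is also reproduced with two conditions at rho = .65. The documents give no rho, so the figure cannot be checked from them.

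**Effect size.** If one condition differs from the other two by delta, f = delta x sqrt(2)/3, so delta = .25 x 3 / 1.414 = .530 SD.

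**What each rule detects.** N = 40, rho = .5. For the overall test lambda = 7.5 / .5 = 15 and power is 93.5%. The contrast figures are from simulated paired t tests, two-sided .05, counted only when C is lower.

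| True pattern | Overall test | C below A and B | (A+B)/2 versus C |
|---|---|---|---|
| Only C below placebo | 93.5% | 84% | 97% |
| Only B below placebo | 93.4% | 0% | 0% |
| B and C equally below placebo | 93.8% | 2.5% | 47% |

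The overall test responds the same way in all three rows. The averaged contrast has more power, but is significant in nearly half of trials when the hormones help equally. In that third row C-A alone is significant in about 90% of trials, correctly, because P4 does work there.

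**Power if E2 is partly protective.** A-C is kept at .530 SD, so B-C is .530, .398 (= .75 x .530) or .265 (= .5 x .530).

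| rho | Both contrasts: E2 no effect | E2 a quarter of P4 | E2 half of P4 |
|---|---|---|---|
| .3 | 67% | 49% | 27% |
| .5 | 84% | 66% | 37% |
| .7 | 98% | 88% | 56% |

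C-A alone at rho = .5 has about 90%. Holding f at .25 instead would give 76% and 47% at rho = .5, but only by enlarging A-C to .588 and .612 SD.

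**Two endpoints.** If either overall test at .05 suffices, the false-positive rate is up to 1 - .95^2 = 9.75%. If both must succeed, there is no inflation.

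**The case against.** **The comparisons are stated in advance.** Their direction is given in 2.2, 4.1 and 10.2, and 2.2 and 4.1 leave room for contrasts. Section 10.4.2 never uses the word omnibus. This is fair: the gap is not that the hypothesis is missing. But no section says which contrast decides the result, and with a general null, a general power statement and no SAP to follow, a general test is the natural reading.

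**The endpoint may already include B versus C.** A reader might infer from the formula that this comparison is left out of the trial. The documents do not support that: the Protocol Summary, 10.2 and 10.4.2 all carry wording that covers it. What stands is a conflict between the formula and that wording.

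**Requiring both contrasts for any P4 claim would be too strict.** This stands. Sections 3 and 4.1 also ask whether P4 stabilization lowers risk at all, which C-A answers. A both-contrasts rule applied to that question would suppress a true effect when B and C help equally (2.5% against about 90%). The two claims need separate rules.

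**The averaged contrast is a possible reading**, since 2.2 groups A and B against C. It remains open to the sponsor, within the limit shown above.

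**The figures are normal-theory**, while 10.4.1 expects nonparametric tests. This limits their precision. It does not change the fact that an overall test of either kind does not identify the hormone.

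**Conclusion.** The concern holds as a mismatch between the claim and the test, and as a missing decision rule. The design can answer the question, but the written plan does not commit to asking it. At the assumed N = 40, f = .25 and rho = .5, the overall test is significant in about 93.5% of trials whichever hormone acts, so it carries no information on the contrast between P4 and E2. Across the two endpoints the false-positive rate of the overall tests could reach 9.75% if either suffices.

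A reader might go further and infer that 24 participants is wrong or that the trial is too small. The documents do not show this. The figure depends on an unstated correlation and on a cited source not available here, and 40 completers give 84% for both contrasts at rho = .5 if E2 has no effect. What can be said is that the stated power is not shown to be the power of the hypothesized comparison, and that the latter falls quickly if E2 is partly protective, as section 3 predicts.

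The sizes rest on the assumed correlation, effect pattern and normality. They do not reflect carry-forward, covariates or nonparametric tests.

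**What to change.** - **10.4.2:** for each primary endpoint, name two primary contrasts and tie each claim to them. C-A significant at two-sided .05 with C lower supports the claim that P4 stabilization reduces risk relative to placebo. C-A and C-B both significant with C lower supports the claim that P4 withdrawal drives risk more than E2 withdrawal. If the averaged contrast is preferred, say so and do not claim P4 specificity from it alone. Use the same paired contrasts if the nonparametric route is taken.
- **4.2.1:** add B minus C, so that the formula agrees with the Protocol Summary, 10.2 and 10.4.2. Reconcile the outcome, which is the final seven days in 4.2.1, the Lab 2 minus Lab 1 change in 10.2, and the mean during each condition in 10.4.2.
- **10.4.9:** state whether one or both primary endpoints must succeed, and how alpha is handled if one suffices.
- **10.5:** restate power at 40 completers for the chosen contrasts, with a stated correlation (the preceding study could supply one) and a stated E2 effect. Reconcile the 30 participants in the power paragraph of 4.1 with the 40 completers in 2.2, 10.5 and the participants paragraph of 4.1.

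**Cost.** Text changes only: no new visits, data or participants. The stated power becomes less favourable than the overall test's 93.5%, by the amounts tabulated above.
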